## 11.0 Specimen Collection and Banking (if applicable)

- Urinary pregnancy tests (obtained per standard of care per IPLEDGE requirements and per the clinical care team) may be collected at each participant's clinic visits in the MUSC outpatient dermatology clinic. For virtual follow-up visits, per current standard of care by IPLEDGE during COVID-19 pandemic, females can also take a home pregnancy test and label with name, date, and time and submit a photo of the test through MyChart (Epic). Pregnancy test results will be obtained from the medical record. Laboratory blood work will be drawn through either the MUSC lab or through LabCorp so that results will be automatically uploaded into the patient's Epic medical chart. No specimens will be collected or kept by investigators.

## 12.0 Data Management

- Participant clinical photos, signed consent form, and photos or scans of their completed surveys will be uploaded into the Media tab of Epic electronic health record either in clinic or by the patient through MyChart. Laboratory result information will result in the patient's Epic medical chart. This will keep this information secure and protected. Study team members will have permission to access study participants' medical records for the purpose of retrieving information for the study, as listed in the study consent form.
- Data Retriever will securely email ("send secure") the participant photos (deidentified) to the Photo Reviewer to score. This will occur over MUSC email only.
- Storing of synthesized study information (participant follow-up dates, scoring of clinical photos, list of any participant lab abnormalities, participant survey answers) will be entered in an encrypted Excel sheet, labeled only with participant number and without patient identifiers (**attachment F**). Only investigators directly involved with the study will have access to this encrypted Excel sheet.
- Paper consent forms will be stored in a locked office (Rutledge Tower, dermatology office floor 10). Electronic consent forms will be stored on a MUSC desktop computer that is secured by username and password. Photos of all consent forms will be taken for upload into patient's Media tab in their medical chart.
- Since this is a proof-of-concept study, there will not be any statistical analysis. Observations will be reported.
- Data will not leave MUSC.

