## 1. Objectives / Specific Aims

The objectives of the study are to:

- determine if once weekly dosed isotretinoin is effective for moderate acne vulgaris
- evaluate patient satisfaction with once weekly dosed isotretinoin for moderate acne vulgaris treatment
- identify any adverse effects associated with once weekly dosed isotretinoin for moderate acne vulgaris treatment

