### 4.0 Study Endpoints (if applicable)

Primary endpoint: efficacy

Secondary endpoints: patient satisfaction, adverse effects

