## **6.0 Number of Subjects**

Target enrollment is 50 participants to allow for attrition. Minimum expected enrollment is 30 participants.

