## 10.0 Study Design / Methods

This will be an open-label, prospective, proof-of-concept study of patients with moderate inflammatory acne. The patients will be treated for at least 4 months.

- The initial acne assessment will be performed by dermatologists and dermatology residents using a validated, clinical grading system (Comprehensive Acne Severity Scale, CASS as below) with lesion counts (inflammatory and noninflammatory). Only moderate acne patients who are eligible for enrollment will be allowed to participate. Recruitment methods are outlined in above section 8.0. A baseline photo will be taken and placed in the patient's medical chart (Epic).

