- The Study Coordinator (Dermatology research fellow), who per the study consent form has permission to access participants’ medical records for the purpose of the study, will follow each patient through Epic electronic medical record to confirm that photos are submitted in a timely manner.
- A separately trained individual (“Data Retriever”), who per the study consent form has permission to access participants’ medical records for the purpose of the study, will submit any uploaded photos (baseline and at the end of each

month) from Epic to the Photo Reviewer by secure, encrypted email, labeling only with participant number and date of photo. This ensures that the Photo Reviewer is always reviewing only individual photos and will not ever enter the patient's medical chart to further limit bias.

- Photo Reviewer will receive photos and document a monthly CASS grade for each participant (in encrypted Excel only accessible by study team members, using study participant numbers without patient identifiers, **attachment F**). Baseline photos will all be a grade 3 (moderate) based on study inclusion criteria. "Improvement" is defined as decrease in grade from a 3 (moderate) to either a 2 (mild), 1 (almost clear), or 0 (clear). "Failure" is defined as showing no improvement (remaining a grade 3), increasing grade of 4 (severe) or 5 (very severe), or requiring additional oral treatment (for example, worsening acne requiring conventional dose isotretinoin). Treatment success can then be calculated as the percentage of participants with improvement out of the total number of participants at the end of four months, in addition to treatment success after each month of treatment.
- Any participants who take any oral tetracycline antibiotics or trimethoprim-sulfamethoxazole during the study period (for a reason besides acne) will be removed from the study in order to prevent any confounding. Patients requiring these medications for acne after the study period has begun will remain included in the study and will be listed as intervention "failure" as above. Participants will be allowed to continue use of topical acne cleansers and treatments during the study as per standard of care.

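### The protocol rules out statistical analysis, so the success percentage from 30 to 50 patients would carry no measure of uncertainty, although the aim is to determine effectiveness

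*Protocol*

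**What the plan says.** The first objective in section 1 is to "determine if once weekly dosed isotretinoin is effective for moderate acne vulgaris". Section 4.0 gives "Primary endpoint: efficacy" with no further detail. Section 10.0 supplies the measure. A participant improves if the CASS grade falls from 3 to 2, 1 or 0, and the rule reads: "Treatment success can then be calculated as the percentage of participants with improvement out of the total number of participants". This percentage is taken at month 4 and also after each month.

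On size, section 6.0 says "Target enrollment is 50 participants to allow for attrition" and "Minimum expected enrollment is 30 participants". Section 10.0 describes the design: "This will be an open-label, prospective, proof-of-concept study of patients with moderate inflammatory acne". One regimen is given and no control group is described.

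On analysis, section 12.0 says "Since this is a proof-of-concept study, there will not be any statistical analysis", followed by "Observations will be reported". Section 16.0 adds that, if participants benefit, larger randomised studies could follow. Section 17.0 says that results are withheld until they have been analysed, without naming a method.

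**The concern.** This is not a detail left for a statistical analysis plan. The protocol states a rule, and a later plan that provided intervals would contradict it. The rule also sits badly with the first objective: finding out whether a regimen is effective is a question about future patients, not only about those enrolled.

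The reason given supports only part of the rule. A proof-of-concept study can properly do without a hypothesis test and a power calculation. When there is no test, the interval is the main protection against over-reading a percentage from a small group. Without it, a majority response could be taken as established when the data are also compatible with a response in fewer than half of patients.

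The same applies to safety. Identifying adverse effects is a stated objective, and sections 15.0 and 16.0 expect risks no greater than with conventional dosing. Seeing no case of an effect in a few dozen patients could be taken as more reassurance than it gives.

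**Working it through.** **Inputs from the protocol.** Target 50 and minimum 30 (section 6.0); a binary outcome, improved or not (section 10.0).

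**Inputs assumed.** The protocol gives no expected success rate, reference rate, precision target or dropout rate. Observed rates of 50% to 90% are therefore used as a range, and 30 and 50 are taken as the numbers analysed. If attrition reduces the number analysed below enrolment, the intervals widen.

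**The protocol's own figure.** The sample size of 50 cannot be reproduced, because nothing is given from which to derive it. The only arithmetic available is 1 − 30/50 = 40% attrition, and that holds only if 30 is read as the number completing, which section 6.0 does not say.

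**Success percentage.** For x successes out of n, the exact (Clopper-Pearson) 95% limits are

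- lower: the 0.025 quantile of Beta(x, n − x + 1)
- upper: the 0.975 quantile of Beta(x + 1, n − x)

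| Observed rate | n = 50: count, 95% interval | Width (points) | n = 30: count, 95% interval | Width (points) |
|---|---|---|---|---|
| 50% | 25/50, 35.5–64.5% | 28.9 | 15/30, 31.3–68.7% | 37.4 |
| 60% | 30/50, 45.2–73.6% | 28.4 | 18/30, 40.6–77.3% | 36.7 |
| 70% | 35/50, 55.4–82.1% | 26.7 | 21/30, 50.6–85.3% | 34.7 |
| 80% | 40/50, 66.3–90.0% | 23.7 | 24/30, 61.4–92.3% | 30.9 |
| 90% | 45/50, 78.2–96.7% | 18.5 | 27/30, 73.5–97.9% | 24.4 |

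(For 25/50 the unrounded upper limit is 64.47%, hence 64% in whole numbers.)

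Wilson intervals are slightly narrower: over the same rates, 17 to 27 points wide with 50 patients and 22 to 34 with 30. The message does not depend on the method.

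One half serves here only as a familiar yardstick; the protocol sets no threshold. At an observed 60%, the lower limit is below half at both sizes. At 70%, it is above half at both, but with 30 patients only just.

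**Adverse effect with no case seen.** The upper limit of the two-sided exact 95% interval is 1 − 0.025^(1/n):

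- n = 50: 1 − 0.025^(1/50) = 7.1%
- n = 30: 1 − 0.025^(1/30) = 11.6%

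With a one-sided 95% limit, 1 − 0.05^(1/n), these become 5.8% and 9.5%.

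**DLQI.** It is collected at baseline and at each monthly visit (section 10.0), so a paired change can be computed. The protocol gives no standard deviation, so no width is calculated here.

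**The case against.** The strongest reply is that this is a declared design choice. The study is labelled proof of concept, the protocol gives that as its reason, and section 16.0 leaves further evidence to larger randomised trials. In context, the sentence in section 12.0 may well mean only that no tests will be done. A reader given the numerator and denominator can compute the interval, and reporting can be corrected after the data are in. These points stand, and they limit the weight of the concern. They do not remove it: the sentence as written excludes all statistical analysis, and nothing elsewhere provides for a measure of uncertainty.

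A second reply is that sampling error is the smaller threat to the aim. There is one regimen and no control group, topical treatments continue, and everyone enters at grade 3, so regression to the mean is possible. This is right. An interval could not show that the drug caused the improvement, and the fix must say so.

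Three stronger readings are tempting, and the document does not support them:

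- *Nothing will be summarised.* Section 10.0 plans success percentages at month 4 and monthly; what is missing is their uncertainty.
- *Quality of life would have no estimate of change.* No such summary is specified, but nothing bars a descriptive one.
- *A go/no-go decision rests on the point estimate alone.* Section 16.0 says only that larger studies can follow if benefit is seen. It sets no threshold and no formal decision rule.

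**Conclusion.** The concern holds as a reporting gap that should be closed. The stated rule leaves the primary percentage without an interval, while the first objective asks for a conclusion about effectiveness. For observed rates of 50% to 90%, the unreported exact 95% interval is 18.5 to 28.9 points wide with 50 patients and 24.4 to 37.4 with 30. That is enough to change how a result near 60% is read.

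The size rests on assumed success rates and on 30 or 50 patients analysed. The finding itself does not: any rate in this range at these numbers gives a wide interval. It is not a flaw in data collection, and it does not call for a hypothesis test or a larger sample.

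**What to change.** Replace the sentence in section 12.0 with wording such as:

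> No hypothesis test is planned. Success at month 4 (primary) and at each month, and each adverse effect, will be reported as numerator, denominator and proportion with an exact (Clopper-Pearson) 95% confidence interval, using one stated denominator. Change in DLQI from baseline to month 4 will be reported as a paired change with a 95% confidence interval. As there is no control group, the intervals describe sampling error only.

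The denominator has to be settled at the same time. Section 10.0 refers to the total number of participants, yet removes those who take certain antibiotics for reasons other than acne, and section 14.0 allows withdrawal at the investigators' discretion. An exact interval on an unsettled denominator would give false precision.

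Reword the first objective in section 1 as estimating the improvement rate on the regimen, which is what a single-group design can deliver. Rewording alone would ease the conflict with the aim, but would still leave the percentage without its uncertainty, so both changes are worth making.

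The cost is a few sentences and slightly more analysis. The result may look less favourable with its interval attached. No patients, visits or data are added.

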### **13.0 Provisions to Monitor the Data to Ensure the Safety of Subjects (if applicable)**

- Data Retriever (as above), the Principal Investigator, and the Study Coordinator will serve as a data monitoring committee. At the end of each month, Data Retriever will review each participant's laboratory blood work results and surveys and input the information into the encrypted Excel sheet. This Excel sheet will be reviewed by the rest of the data monitoring committee. The clinicians that see each participant will also review laboratory blood work as it is completed and are instructed to notify the investigators with any significant abnormalities as they arise. Any pertinent abnormalities (elevated liver enzymes, elevated triglycerides) will be discussed with the patient by their individual providers and the decision to continue or discontinue isotretinoin will be a joint patient-provider decision made at that visit based on clinical judgement. Additionally, any clinically significant baseline laboratory abnormalities will exclude the patient from enrolling in the study. If the patient's liver enzymes or triglycerides increase to > 3 times the upper limit of normal during the study period, the medication will be stopped.

### **14.0 Withdrawal of Subjects (if applicable)**

- Study investigators may withdraw a participant from the study at any time at their discretion. Circumstances can include when a participant's safety may be compromised such as when a participant is experiencing adverse events requiring discontinuation of the drug, if the study is stopped in relation to risk to participants, or when the participant is non-compliant with the medication regimen.
- A study investigator will inform the participant that he or she has been withdrawn from participation and the reasons therefore.

- At any time, a participant can withdraw from participation in some or all components of the study.
  - When the participant withdraws, the participant will no longer receive isotretinoin at the experimental regimen.
  - The participant's medical record or other confidential records will not be accessed by the investigator.
  - The data collected to the point of withdrawal will remain part of the study records.
- At a minimum, documentation of the participant's withdrawal will include the date, rationale, and which component the participant is withdrawing.
- The Primary Investigator will inform the IRB of the number of participants who withdrew and the reason for withdrawal.

## **15.0 Risks to Subjects**

- There is a risk of a loss of confidentiality of personal information as a result of participation in this study which will be mitigated at all costs by the study team members.
- There is a risk to embryos of females who become pregnant while on isotretinoin. The participant will be educated extensively on these risks and enrolled in the IPLEDGE program which per standard of care requires two forms of birth control for females of child-bearing potential while on isotretinoin, pregnancy tests at baseline, pregnancy tests each month while on the medication, and again one month after stopping the medication.
- Risks to participants include those that are present when taking isotretinoin at the conventional, higher dose. Potential side-effects of isotretinoin include dry skin, dry mucous membranes (lips, eyes), GI upset, bone or muscle pain, night vision abnormalities, mood swings/depression, headaches, delayed wound healing, and laboratory abnormalities (namely hypertriglyceridemia, elevated liver enzymes). Frequent monitoring by the patient's clinician and monthly monitoring by the data monitoring committee will take place to minimize risks to participants (detailed in section 13.0). These participants will be taking isotretinoin only once weekly, at a dose equivalent of what patients usually take once daily; study dose is 1/7 of the usual, weekly total dose. Because of this, we have reason to believe that risks will be either the same or less than risks while on conventional dose isotretinoin.
- There is a risk of emotional distress when filling out the monthly surveys. If the participant admits to feeling depressed thoughts, the participant will be given the appropriate resources and a psychiatric referral can be placed if the patient wishes. If the patient admits to suicidal or homicidal ideation, inpatient psychiatry will be consulted.

## **16.0 Potential Benefits to Subjects or Others**

- Potential benefit of intervention is improvement in participants' moderate acne vulgaris. There is benefit of minimal dosing, as well as avoidance of long-term antibiotics (and of antibiotic resistance).

- An additional potential benefit is contributing to furthering medical knowledge regarding isotretinoin and moderate acne. If participants show a benefit to this alternative isotretinoin dosing, further larger and randomized studies can be completed.
- Risks are reasonable in relation to the anticipated benefit to participants. Risks to participants include those that are present when taking isotretinoin at the conventional, higher dose (detailed in section 15.0). These participants will be taking isotretinoin only once weekly, at a dose equivalent of what patients usually take once daily; study dose is 1/7 of the usual, weekly total dose. Because of this, we have reason to believe that risks will be either the same or less than risks while on conventional dose isotretinoin.

### **17.0 Sharing of Results with Subjects**

- Because this is an open-label study, all participants will know what medication they are taking and at what dose.
- Information such as standard of care lab results will be returned to the patient once of the results are available. Abnormal results will be followed up by the patient's clinician and data monitoring committee.
- Results regarding the participants and overall response to the medication will be withheld during the study until the results are analyzed.

### **18.0 Drugs or Devices (if applicable)**

- Isotretinoin (study drug) will be prescribed to each participant through Epic electronic medical record. The medication will be paid by each patient's insurance or by self-pay (per MUSC Rutledge Tower Pharmacy, this dosing should be covered by most insurance plans and is otherwise \$10.36 for a 40 mg isotretinoin pill). The participant will directly pick up the medication each month from the pharmacy and will store the medication at home in a safe, shaded, secure place. The investigators and study team will not handle or store any study drug.

### **References**

All references are noted and listed by number under their respective sections.

All attachments are noted and listed by letter within the text and highlighted in yellow.
